4.2 Rationale for dose/regimen and duration of treatment

Preliminary, publicly available data suggest efficacy of mavrilimumab at a dose of 6 mg/kg IV. However, these results are from an open-label study, and the results from our Phase II randomized, placebo controlled trial may inform the design and dose for larger studies.

In a Phase 1 single-ascending-dose (SAD) study, the pharmacokinetics (PK) of mavrilimumab were tested at doses of 0.01-10 mg/kg in patients with mild-to-moderate RA. Mavrilimumab was well-tolerated in a single IV injection up to 10 mg/kg in subjects with mild to moderate RA at all dose levels. Pharmacokinetic and pharmacodynamic simulations from studies in subjects with RA, coupled with the PK data from the Phase 1 study, indicate that a single dose of ≥ 3 mg/kg will provide EC90 (the concentration that leads to 90% maximal response) for the RA endpoint ACR50 (American College of Rheumatology 50% response criteria; data on file) for up to 22 days. Therefore, at doses ≥ 3 mg/kg, the pharmacologic profiles indicated sustained peripheral inhibition of the GM-CSF-R α signaling axis for at least three weeks.

In preclinical studies, the potential systemic effects of mavrilimumab (CAM-3001) have been investigated in a 4-week and an 11-week repeat dose cynomolgus monkey study. There were no effects attributable to intravenous (IV) administration of CAM-3001 (mavrilimumab) in doses up to 100 mg/kg/week for 4 weeks in a study conducted in accordance with Good Laboratory Practice (GLP). In an 11-week exploratory (non-GLP) study, there were no effects attributable to IV administration of CAM-3001 (mavrilimumab) following 10 mg/kg/week, and the no observed adverse event level (NOAEL) was 100 mg/kg/week. An immunocytochemistry screen to test in vitro binding of CAM-3001 (mavrilimumab) to a panel of normal human tissues revealed no non-specific or unanticipated binding of the antibody. Reference for further details on safety studies in animals and humans is made to the investigator brochure.

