4.3 Risks and benefits

To date, there are no adverse events with a recognized causal relationship to exposure to mavrilimumab. However, there are a number of hypothetical risks that can be extrapolated from the mechanism of action. In particular, GM-CSF antagonism may interfere with immune response to infections. It is unknown how likely these effects are to occur, but their frequency may be lower with a one-time dose as compared to a longer duration to treat a chronic disease.

Frequent side effects:

- Nausea (approximately 1 in 10 subjects, self-limiting)
- Nasopharyngitis (approximately 1 in 10 subjects, self-limiting)
- Headache (approximately 1 in 10 subjects, self-limiting)

Rare but potentially life-threatening adverse reaction:

- Severe hypersensitivity reactions: While these have not been reported with Mavrilimumab, such reactions (including anaphylaxis, anaphylactoid reactions, cytokine release, and endotoxemia) have been observed after administration of other monoclonal antibodies. These reactions may be severe and may result in death.
- Leukopenia resulting in an increased risk of opportunistic infections. Mavrilimumab reduces the number of neutrophils. In some patients the reduction may be such to expose to additional (opportunistic) infection.

Additional potential side effects (of unknown frequency):

- Pulmonary alveolar proteinosis (PAP): studies have linked blockage of GM-CSF, the target of Mavrilimumab, with PAP. While the use of Mavrilimumab has not been

associated with the development of PAP in patients, a potential risk for this complication with Mavrilimumab use may exist.

- While the use of Mavrilimumab has not been associated with the development of cancer, drugs that modulate the immune response may increase the risk of cancer.
- Impaired response to vaccines. Drugs that reduce the immune response, like Mavrilimumab can impair the immune response to vaccine.
- Antibodies that inactivate the study drug thus losing its efficacy

In general, the risk to subjects in this trial may be minimized by compliance with the eligibility criteria and study procedures, close clinical monitoring, as well as periodic review of all safety data by an independent data monitoring committee (DMC).

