5.2 Exclusion criteria

Subjects meeting any of the following criteria are not eligible for inclusion in this study:

1. Onset of COVID-19 symptoms >14 days
2. Age < 18 years-old
3. Hospitalized >7 days
4. Mechanically ventilated
5. Serious concomitant illness which in the opinion of the investigator precludes the patient from enrolling in the trial, including (but not limited to):
 - History of immunodeficiency (congenital or acquired)
 - Neutropenia (absolute neutrophil count <1,500/mm³)
 - History of solid-organ or bone marrow transplant
 - History of current systemic autoimmune or autoinflammatory disease(s) requiring systemic immune-modulating drugs
 - History of myeloproliferative disorder or active malignancy receiving cytotoxic chemotherapy
 - Pre-existing severe pulmonary disease (i.e. steroid dependent asthma, COPD on home oxygen, or other restrictive/obstructive lung disease requiring home oxygen)
 - Pre-existing severe left ventricular systolic dysfunction (i.e. LVEF <35%)
 - Known or suspected active tuberculosis (TB), latent TB, or history of incompletely treated TB or at high risk for latent TB (from exposure or prior incarceration)
 - History of active or latent viral hepatitis (i.e. Hepatitis B or C)
 - Concomitant uncontrolled systemic bacterial or fungal infection
 - Concomitant viral infection other than COVID-19 (e.g. Influenza, other respiratory viruses)
 - History of chronic liver disease with portal hypertension
 - History of end-stage renal disease on chronic renal replacement therapy
6. Recent treatment with cell-depleting biological therapies (e.g., anti-CD20) within 12 months, cell-depleting biological therapies (such as anti-tumor necrosis factor [TNF], anakinra, anti-Interleukin [IL]-6 receptor [e.g. tocilizumab], or abatacept) within 8 weeks (or 5 half-lives, whichever is longer), treatment with alkylating agents within 12 weeks, treatment with cyclosporine A, azathioprine, cyclophosphamide, or mycophenolate mofetil (MMF) within 4 weeks
7. Recent treatment with intramuscular live (attenuated) vaccine within 4 weeks
8. Chronic or recent corticosteroid use > 10 mg/day
9. Pregnant and breast-feeding women
10. Enrolled in another investigational study using immunosuppressive therapy
11. Known hypersensitivity to mavrilimumab or any of its excipients

12. In the opinion of the investigator, unable to comply with the requirements to participate in the study

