7.1 Visit schedule and assessments

The assessment schedule lists all of the assessments and indicates with an “X”, the visits when they are performed. All data obtained from these assessments must be supported in the subject’s source documentation.

Subjects should be seen for all visits/assessments as outlined in the assessment schedule or as close to the designated day/time as possible. Missed or rescheduled visits should not lead to automatic discontinuation. Subjects who prematurely discontinue the study for any reason should be scheduled for a visit as soon as possible, at which time all of the assessments listed for the final visit will be performed.

Clinically significant abnormalities must be recorded on the relevant section of the CRFs capturing medical history/current medical conditions/AE as appropriate.

Table 7-1 Assessment Schedule^{tt}

Activity	Study Day ^a													Unscheduled ^d
	-3 to 0 ^b	0	1	2	3	4	5	6	7	14	21	28 ^c	60	
Informed consent	X													
Demographics	X													
Reason for hospitalization (COVID-19 pneumonia)	X													
Medical history	X													
Eligibility	X													
Physical exam	X													X
Vital signs	X	X	X	X	X	X	X	X	X	X	X	X	X	
Body Temperature (Celsius)	X	X	X	X	X	X	X	X	X	X	X	X	X	
Body weight	X													
Height	X													
Electrocardiogram	X													X
Chest imaging (CXR or chest CT)	X													X
Clinical assessment (6 category ordinal scale) ^a	X	X	X	X	X	X	X	X	X	X	X	X	X	
SOFA score	X								X	X	X	X	X	
2019-nCoV test*	X								X	X	X	X	X	
Respiratory Virus Panel	X													
CRP	X	X	X	X	X	X	X	X	X	X	X	X	X	
LDH ^e	X	X	X	X	X	X	X	X	X	X	X	X	X	
D-Dimer ^e	X	X	X	X	X	X	X	X	X	X	X	X	X	
Ferritin ^e	X	X	X	X	X	X	X	X	X	X	X	X	X	
Troponin	X													
NT-proBNP	X													
Mechanical ventilation assessment	X	X	X		X		X		X	X	X	X	X	
Respiratory parameters ^g	X	X	X		X		X		X	X	X	X	X	

Activity	Study Day ^a													
	-3 to 0 ^b	0	1	2	3	4	5	6	7	14	21	28 ^c	60	Unscheduled ^d
TB screening ^h	X													
Pregnancy test ⁱ	X													
Hematology (CBC + diff)	X				X					X				X
Coagulation (PT, PTT, INR)	X													
Chemistry (lytes, BUN, glucose, CR)	X				X					X				X
Liver profile (AST, ALT, Alb, AlkP, Tbili, Dbili)	X			X					X					X
Urinalysis	X													X
Adverse events	X	X	X	X	X	X	X	X	X	X	X	X		X
Concomitant medications ^l	X	X	X	X	X	X	X	X	X	X	X	X		X
Assessment for “off of oxygen” as defined for the primary endpoint ^o														

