Assessment for “respiratory failure” as defined for the secondary endpoint														X
Assessment of survival (day of death if occurs) ^m	X											X	X	
Mavrilimumab/placebo administration		X												

^a Given resource limitation related to COVID-19, all laboratory testing is considered standard of care, though as possible, certain tests that are not considered standard of care may be obtained for research. If the laboratory tests in the schedule of activities are obtained, they will be documented accordingly. If laboratory tests cannot be obtained for other reasons, such as requiring extra use of personal protective equipment, unnecessary exposure to healthcare personnel, or safety issues related to obtaining and processing samples, these will not be considered a protocol deviation.

^b Study visits are planned for hospitalized patients only; planned activities that fall on study days that occur after the patient is discharged will not be done.

^c Screening activities can occur from -3 and 0 days before enrollment except for 2019-nCoV testing, which can occur between -7 and 0 days before enrollment.

^d For hospitalized patients, this visit will include the activities listed. For patients who have been discharged before Study Day 28, this visit will be conducted by phone/telehealth but will not include any laboratory tests.

^d An unscheduled visit is planned to occur on the day of discharge if the patient is discharged before Day 28; in which case this will serve as an early termination visit. If patient is discharged the visit on Study Day 28±3 and Study Day 60±3, will be done by telephone call follow-up and lab tests will not be performed. May also be used for adverse event assessments.

* Nasopharyngeal or oropharyngeal swabs for SARS-CoV2 RNA levels will be performed until negative or discharge. Sampling will include both nostrils, or repeat sampling will include the same nostril if only one nostril is used. A local sample will be used for inclusion criteria, and as possible appreciating the concerns related to extra use of personal protective equipment and exposure to healthcare personnel

"For the purposes of the primary end-point and time to freedom from supplemental oxygen, the ordinal scale and presence of supplemental oxygen will be assessed daily thru Day 14 while hospitalized. If patient has been discharged prior to Day 14, it will be assessed on Day 14, 21 and 28.

^e Collect at least baseline and at least weekly thereafter.

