^g Includes FiO₂, SpO₂, Respiratory rate, note if ventilated or not, if yes collect PEEP; rescue therapy used (e.g., Flolan, proning, NM blockade, ECMO). For FiO₂, SpO₂, and PEEP, best and worst of daily value. Calculate P to F ratio best and worst for each day.

^h Done at Investigator's discretion; not expected to be used for decision to treat; not a mandatory test.

ⁱ Females of child-bearing potential only, urine or serum at investigator's discretion.

^j Includes complete blood count (CBC) and differential at screening and CBC on subsequent indicated days.

^l Prohibited medications include any cell-depleting biological therapies (e.g., anti-CD20) within 12 months prior to Day 0; or previous treatment with noncell-depleting biological therapies (such as anti-tumor necrosis factor [TNF], anakinra, anti-Interleukin [IL]-6 receptor [e.g. tocilizumab], or abatacept) within 8 weeks (or 5 half-lives, whichever is longer) prior to Screening, treatment with alkylating agents within 12 weeks prior to Screening, intramuscular, receipt of live (attenuated) vaccine within the 4 weeks before Day 0, treatment with cyclosporine A, azathioprine, cyclophosphamide, or mycophenolate mofetil (MMF) within 4 weeks of Screening. **Concomitant medications to track include: antipyretics, antibiotics related to secondary infections, and all investigational off-label therapies for COVID-19 for each subject (e.g. chloroquine, hydroxychloroquine, anti-IL-6, corticosteroids, remdesivir, lopinavir/ritonavir) along with time, dose, and duration of their administration.** Other concomitant medications will be recorded at baseline and daily thereafter while hospitalized until Day 7, at Day 14, Day 21 and Day 28. This information will be included in the final study report.

^o Assessed daily thru Day 14 if hospitalized. If the patient is discharged, assess at Day 14.

^m Document whether death occurred after withdrawal of care, and if so, reason for withdrawal of care.

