7.2.1 Laboratory evaluations

Pre-treatment screening will include:

- Complete blood count (CBC), serum biochemical tests (including renal and liver function), troponin, NT-proBNP, albumin, total protein, coagulation profile, D-dimer, fibrinogen, LDH, CRP, serum ferritin, IL-6, quantiferon (optional), serum lipid panel (triglycerides), 2019-nCoV test.

On-treatment measurements (as noted in the schedule of activities):

- Complete blood count (CBC), serum biochemical tests (including renal and liver function), albumin, total protein, coagulation profile, D-dimer, LDH, CRP, serum ferritin, IL-6, 2019-nCoV test

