9.1.6 Data Monitoring Committee

This study will include a data monitoring committee (DMC) which will function independently of all other individuals associated with the conduct of this clinical trial, including the site investigators participating in the study. The DMC will assess at defined intervals the progress

of a clinical trial, safety data, and critical efficacy variables and recommend to the sponsor/investigator whether to continue, modify or terminate a trial.

Summary reports will be provided to a DMC after the first 5 subjects have been reviewed, after 15 subjects have been reviewed, and after every 10 subsequent patients.

Specific details regarding composition, responsibilities, data monitoring and meeting frequency, and documentation of DMC reports, minutes, and recommendations will be described in a separate charter that is established between the sponsor/investigator and the DMC.

Schedule of Safety Assessments:

Data Collection and Database management

Activity	Study Day													60	Unscheduled
	-3 to 0	0	1	2	3	4	5	6	7	14	21	28			
Vital signs	X	X	X		X		X		X	X	X	X		X	
Medications	X	X	X						X	X	X	X		X	
Respiratory parameters	X	X	X						X	X	X	X		X	
Hypersensitivity reaction			X	X	X	X	X	X	X						
Anaphylaxis reaction (defined according to Sampson's criteria, Sampson HA et al., J Allergy Clin Immunol. 2006 Feb;117(2):391-7		X	X	X											
Secondary Infections	X	X	X						X	X	X	X	X	X	
Hematology (CBC + diff: assessment for leukopenia, neutropenia, and thrombocytopenia)	X				X				X			X		X	
Coagulation (PT, PTT, INR)	X														
Chemistry (lytes, BUN, glucose, CR)	X				X				X			X		X	
Liver profile (AST, ALT, Alb, AlkP, Tbili, Dbili: assessment for drug-induced liver injury according to Hy's law)	X				X				X			X		X	
Adverse events	X	X	X	X	X	X	X	X	X	X	X	X	X	X	

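### Table 7-1 note j limits the white-cell differential to screening, while the hematology row labels call for it after dosing, so the post-dose neutrophil count is not assured

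*Combined protocol and SAP*

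**What the plan says.** Three places in the protocol define the hematology test.

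- **Table 7-1, row label (section 7.1):** "Hematology (CBC + diff", with marks at screening and afterwards.
- **Table 7-1, note j (section 7.1):** "Includes complete blood count (CBC) and differential at screening and CBC on subsequent indicated days". The superscript that ties the note to a row is not visible in the text available, but only the hematology row fits its content.
- **Schedule of Safety Assessments (section 9.1.6):** "Hematology (CBC + diff: assessment for leukopenia, neutropenia, and thrombocytopenia", again with marks after dosing.

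Four other places bear on how much this matters. Section 4.3 says "Mavrilimumab reduces the number of neutrophils" and links this to opportunistic infection. Section 4.2 expects a single dose of at least 3 mg/kg to inhibit the "signaling axis for at least three weeks"; the trial dose is 6 mg/kg. Section 5.2 gives a numeric definition, "Neutropenia (absolute neutrophil count" below 1,500/mm³, as an exclusion criterion. Note a to Table 7-1 treats laboratory tests as standard of care and does not count a test that could not be obtained as a deviation.

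**The concern.** Note j provides the neutrophil count before the infusion and drops it afterwards, when the drug could lower it. A site that follows the note would have a baseline count and no scheduled count to compare with it. Section 9.1.1 has clinically significant laboratory abnormalities found by review against normal ranges and by change from baseline or the previous visit. For neutrophils that review needs a post-dose differential.

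Safety is a stated secondary objective, and section 4.3 relies on close monitoring and data monitoring committee review to limit risk. What is at stake is whether a fall in neutrophils in an individual patient is seen and recorded.

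**Working it through.** The plan gives no figure to reproduce here. The check is a comparison of texts, a count of marks and one small piece of arithmetic.

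**Step 1: set the texts side by side.**

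| Source | Screening | After dosing |
|---|---|---|
| Table 7-1 row label | CBC + differential | CBC + differential |
| Table 7-1 note j | CBC + differential | CBC only |
| Section 9.1.6 safety row | CBC + differential | CBC + differential |

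Two labels agree and the note departs from both, so Table 7-1 also disagrees with itself. The protocol has no rule of precedence between the two tables. This step does not depend on how the table columns align.

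**Step 2: ask whether a plain CBC can serve the stated purpose.** The absolute neutrophil count is the total white count multiplied by the neutrophil share. A plain CBC gives the first factor and not the second. The share at which a patient crosses the section 5.2 threshold is 1,500 divided by the total white count. The totals below are assumed, since the documents give none:

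- total 3,000/mm³: 1,500 / 3,000 = 50%
- total 4,000/mm³: 1,500 / 4,000 = 37.5%
- total 5,000/mm³: 1,500 / 5,000 = 30%

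A total in this range therefore does not settle whether the patient is neutropenic. The CBC can still show leukopenia and thrombocytopenia, the other two conditions named in the safety row.

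**Step 3: count the marks, as the tables appear in the text available.**

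| Row | Table 7-1 | Section 9.1.6 |
|---|---|---|
| Hematology | 4 | 5 |
| Chemistry | 4 | 5 |
| Liver profile | 4 | 5 |
| Coagulation | 1 | 1 |

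Removing the screening mark leaves 4 − 1 = 3 against 5 − 1 = 4 in each of the first three rows. For hematology under note j, 0 of the 3 later marks in Table 7-1 include a differential; by its label, the safety schedule has 4 of 4.

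**Step 4: weigh how reliable the count is.** A shifted column would not change a count, but a lost mark would. Table 7-1 has visibly lost marks: the row for the off-oxygen assessment is empty, although its own note requires daily assessment through Day 14 in hospital. The 4-against-5 difference is therefore a reason to check the source tables and does not prove that the schedules differ.

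**The case against.** The strongest reply is that the protocol already asks for the differential twice, in two row labels, and that a site need only draw it on the indicated days to satisfy everyone. Many hospitals may run a differential routinely. Note a, which covers the case "If laboratory tests cannot be obtained for other reasons", shows that the trial meant to be flexible about laboratory work. Some of this stands: the conflict lies in one footnote, and the practical effect may be small at sites that order differentials anyway. But note a excuses tests that could not be obtained. It does not put back a test that note j leaves out. It also says that scheduled tests, if obtained, are to be documented, so a routine differential outside the schedule has no clear requirement to be recorded.

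A reader might infer more than the documents support, in four ways.

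- **Section 7.2.1 confirms the plain CBC.** Its list headed "On-treatment measurements (as noted in the schedule of activities" does say CBC without a differential, but so does its screening list, where note j itself includes one. The term is generic there and supports neither side.
- **The two schedules use different days, with long gaps between counts.** The column positions are uncertain, and the last mark in the safety rows could belong to Day 60 or to the unscheduled visit. Table 7-1's notes limit visits to hospitalized patients and add an unscheduled visit at discharge before Day 28. No gap length can be asserted.
- **A particular set of days should be imposed.** The documents do not support one. For example, neither table as read has a liver profile on Day 14.
- **Neutropenia would go unseen or the trial's results would be compromised.** Unscheduled tests and adverse event reporting remain, and no efficacy endpoint uses these values.

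**Conclusion.** The contradiction over the post-dose differential is real and should be corrected. It rests on reading note j as belonging to the hematology row, which is the only row it fits. Its size is one test component at every post-screening hematology assessment in Table 7-1, potentially for all 60 planned patients while they are in hospital. The consequence is confined to detecting and recording neutropenia in individual patients. The primary and secondary endpoints, the sample size, the significance level and the planned adverse event tabulations in section 10.3.1 do not change.

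The difference in mark counts between the two schedules is a secondary point. It is consistent across three rows, but holds only as far as the extracted tables are complete.

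**What to change.** 1. Reword note j to: *CBC with differential at screening and on all subsequent indicated days.*
2. Record the post-dose absolute neutrophil count in the eCRF.
3. Leave note a unchanged, so that a test that cannot be obtained is still not a deviation.
4. Check the hematology, chemistry and liver rows of Table 7-1 against the section 9.1.6 schedule in the source protocol. If they differ, choose one schedule and use it in both tables. The choice of days is for the sponsor and investigators.

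The cost is the wording of one note and a few more laboratory values to enter for patients still in hospital. The differential comes from the same blood sample as the CBC, so no extra draw or exposure of staff is needed. Item 4 costs a comparison of two tables and, if needed, an edit to three rows.
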